14.0 Sample Size And Power

Based on the SHIFT¹ study, the mean heart rate reduction with IVA is 8 bpm with a standard deviation of 13 bpm. A sample size of 57 in each group will have 90% power to detect a difference in means of 8.0 assuming that the common standard deviation is 13.0 using a two group t-test with a 0.05 two-sided significance level. To account for a projected dropout rate of 15%, 66 subjects will be enrolled in each group (132 total for the study over a 2-year period). Furthermore, we expect that our centers will recruit a cohort that is 75% self-identified African Americans. This number (n=99) will provide 80% power to detect the same effect size when analyzed in African Americans only.

For the safety endpoint (unplanned presentation for medical care), assuming an event rate of 25% at 1 month (estimated based on local hospital readmission rates), our sample size will provide 80% power to detect a doubling of the relative risk. If the Control group event rate is higher there will be greater power; for example, with an event rate of 35% we would have 98% power for risk ratio of 2.0 and 83% power for risk ratio of 1.75.

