1.0 Summary

Prospective, randomized (1:1), placebo-controlled, double blind, study of ivabradine (Corlanor®) begun at the time of discharge from the hospital or observation unit after a stay of < 48 hours from the time of admission, for a total of 28 (+/-2) days in a cohort of predominantly (but not exclusively) African American patients with acute heart failure (HF). The primary endpoint will be change in heart rate from discharge to 28 (+/-2) days. Secondary endpoint will be heart rate change in African Americans from discharge to 28 (+/-2) days. Exploratory endpoints include change in NT-proBNP, change in hs-cTnT each comparing baseline to 28 (+/-2) days. Key safety endpoints will be the rate of unplanned medical care (presentation to ED or urgent care, unplanned hospitalization, unplanned medical office visit) and days alive and out of hospital over the 28 (+/-2) days of treatment.

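### Enrolling 66 per arm leaves about 56 evaluable at the planned 15% dropout, one short of the 57 that Section 14.0 requires; the effect on power is very small

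*Protocol*

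**What the plan says.** Protocol Section 14.0 sizes the trial on the change in heart rate: "A sample size of 57 in each group will have 90% power to detect a difference in means of 8.0". The other inputs given there are an SD of 13.0 bpm in both arms and a two-sample t-test at the two-sided 5% level. Section 1.0 gives 1:1 randomisation. The next sentence of Section 14.0 moves from the number needed to the number enrolled: "To account for a projected dropout rate of 15%, 66 subjects will be enrolled in each group", which it totals as "132 total for the study over a 2-year period".

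The SAP reproduces this text and introduces it as the plan set out in the protocol. Neither document says how the dropout allowance was calculated.

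**The concern.** A dropout rate is normally a share of the patients enrolled. If 15% are lost, 85% remain, so the number to enrol is the number needed divided by 0.85. Multiplying the number needed by 1.15 always gives a smaller figure, because 1.15 is less than 1 / 0.85 = 1.176. The figure of 66 looks like the product of that shortcut.

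What is at stake is whether the paragraph agrees with itself. The enrolment target is there to protect 57 evaluable patients per arm. If it does not do so at the plan's own dropout rate, the power attached to the target is slightly overstated.

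**Working it through.** **Inputs.** From protocol Section 14.0: difference 8.0 bpm, common SD 13.0 bpm, two-sided alpha 0.05, power 90%, 57 per arm needed, dropout 15%, 66 per arm and 132 in total enrolled. From Section 1.0: 1:1 allocation.

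**Step 1: reproduce the 57.** For a two-sample t-test with n per arm, the noncentrality is (8/13) × √(n/2) on 2n − 2 degrees of freedom.

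- n = 57: (8/13) × √28.5 = 3.285, 112 df, power 0.9027.
- n = 56: (8/13) × √28 = 3.256, 110 df, power 0.8976.

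So 57 is the smallest n that reaches 90%, and the plan's figure reproduces.

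**Step 2: what 66 per arm leaves.** Evaluable = enrolled × (1 − dropout).

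- Per arm: 66 × 0.85 = 56.1, about 56, against 57 needed.
- Total: 132 × 0.85 = 112.2, about 112, against 114 needed.
- Highest dropout that still keeps 57: (66 − 57) / 66 = 9/66 = 13.6%. The planned rate implies 66 × 0.15 = 9.9 losses per arm.

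**Step 3: where 66 may come from.**

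| Route | Result | Per arm |
|---|---|---|
| 57 × 1.15 | 65.55 | 66 |
| 57 / 0.85 | 67.06 | 67 (nearest) or 68 (rounded up) |
| 56 / 0.85 | 65.88 | 66 |

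The first row is the only one that goes from the stated 57 to the stated 66. The third also gives 66, and a normal approximation does return 56 per arm, but the protocol states 57.

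**Step 4: the enrolment gap.** 67 × 0.85 = 56.95, which is 57 for practical purposes; 68 × 0.85 = 57.8. Against 66, the gap is 1 per arm (134 in total) or 2 per arm (136 in total), depending on rounding.

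**Step 5: the effect on power.** 90.3% at 57 per arm against 89.8% at 56, a loss of about 0.5 percentage points.

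**The case against.** The strongest objection is materiality. The protocol states power as a whole percentage, and 89.8% rounds to 90%, so the headline claim survives at the precision at which it is made. The dropout rate is itself only a projection, and the discrepancy turns on one patient per arm: nine losses keep 57, ten leave 56. This stands, and it limits the point to a minor correction.

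A second objection is that the 15% could have been meant as a share of the 57 needed, in which case 66 is right by construction. The usual meaning of a dropout rate is against this. So, by inference, is the next claim in Section 14.0, that 99 African American patients give 80% power for the same effect. With all 99 analysed (50 and 49 per arm) exact power is 85.8%. With 99 × 0.85, about 84 (42 per arm), it is 79.6%. The stated 80% fits a 15% loss taken from those enrolled. That is suggestive only, since the protocol does not say how the figure was reached.

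Third, a reader might infer that the plan is shown to have used the wrong formula. The documents do not support that: no formula is given, and 56 / 0.85 also rounds to 66. The mismatch between 66 enrolled and 57 evaluable holds whichever route was taken.

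Fourth, a reader might count the SAP as a second error. The SAP presents the text as the protocol's plan, not as a fresh calculation, so it faithfully copies the same figure and adds no separate fault.

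**Conclusion.** The point holds as a small internal inconsistency. At the plan's own 15% dropout, 66 per arm yields about 56 evaluable patients, one fewer than the 57 that the same paragraph requires. Power is 89.8% instead of 90.3%.

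This rests on two assumptions: that the 15% applies to patients enrolled, and that losses are equal in the two arms. Multiplication by 1.15 is the likely explanation for 66, but it is inferred and the conclusion does not depend on it.

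Two stronger readings should be set aside. A reader might infer that the design was underpowered and needed 136 patients. It was not underpowered in any useful sense, because the power still rounds to 90%, and 136 follows only if 67.06 is rounded up. A reader might also connect the shortfall with the trial's failure to produce a formal comparison. The SAP attributes that to low enrolment, with 19 of the targeted 132 patients in the final cohort; a target differing by 1 or 2 per arm could not have mattered.

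**What to change.** In protocol Section 14.0, replace the dropout sentence with one to this effect: enrolling 66 per arm (132 in total) leaves about 56 evaluable per arm after 15% dropout, which gives about 89.8% power for a difference of 8.0 bpm with an SD of 13.0 bpm. Do not add patients.

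Leave the SAP text unchanged, since rewriting it would make it misquote the protocol; a short note beside it is enough if one is wanted.

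The cost is one sentence and a marginally less favourable stated power. Enrolment and analysis are unaffected.

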5.0 Endpoints

Efficacy:

- Primary - Change in heart rate (Day 28 (+/-2) - baseline), measured by 12-lead ECG and Zio® patch (Day 14 (+/-1) - baseline).
- Secondary - Change in heart rate in self-identified African Americans (Day 28 (+/-2) – baseline), measured by 12-lead ECG and Zio® patch³(Day 14 (+/-1) - baseline).
- Exploratory:
 - 1) Change in NT-proBNP (Day 28 (+/-2) – baseline)
 - 2) Change in hs-cTnT (Day 28 (+/-2) – baseline)

Safety: Presentation for unplanned medical care in any setting within 28 (+/-2) days.

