13.0 Statistical Analysis

The primary outcome (change in heart rate i.e. the value at Day 28 (+/-2) - the value at baseline) will be analyzed as two sample t-test. Secondary outcomes that are continuous variables will be analyzed as two sample t-test. The safety endpoint of unplanned visits will be compared as the number of unplanned medical visits over the study period tested using Poisson regression.

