STATISTICAL ANALYSIS PLAN: OBSERVE-IVA

A Randomized, Double-Blind, Placebo-Controlled Trial
Assessing the Efficacy of Ivabradine Initiated at the
Time of Discharge from the Observation Unit

NCT: 03168529
8/1/2021

[name]
[contact]

Statistical Analysis Plan:

**A Randomized, Double-Blind, Placebo-Controlled Trial Assessing the Efficacy of Ivabradine Initiated at the Time of Discharge from the Observation Unit.
(OBSERVE-IVA)**

NCT: 03168529

The original plan detailed in the protocol is as follows:

13.0 Statistical Analysis The primary outcome (change in heart rate i.e. the value at Day 28 (+/-2) - the value at baseline) will be analyzed as two sample t-test. Secondary outcomes that are continuous variables will be analyzed as two sample t-test. The safety endpoint of unplanned visits will be compared as the number of unplanned medical visits over the study period tested using Poisson regression.

14.0 Sample Size And Power Based on the SHIFT1 study, the mean heart rate reduction with IVA is 8 bpm with a standard deviation of 13 bpm. A sample size of 57 in each group will have 90% power to detect a difference in means of 8.0 assuming that the common standard deviation is 13.0 using a two group t-test with a 0.05 two-sided significance level. To account for a projected dropout rate of 15%, 66 subjects will be enrolled in each group (132 total for the study over a 2-year period). Furthermore, we expect that our centers will recruit a cohort that is 75% self-identified African Americans. This number (n=99) will provide 80% power to detect the same effect size when analyzed in African Americans only.

Unfortunately, formal statistical analysis was not completed due to low sample size. Unfortunately, OBSERVE IVA fell far short of its enrollment goal with just 19 out of a targeted 132 subjects included in the final study cohort. Because of this, we have not developed any abstracts, manuscripts or other publications to date, though we may do so in the future. Of the 19 enrollments, 6 were at Detroit Receiving Hospital, 8 at Sinai-Grace Hospital, 2 at Harper University Hospital, and 3 at Henry Ford Hospital. A total of 13 subjects (68%) received ivabradine (IVA) and 6 received matching placebo.

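### The stated safety powers (80%, 98%, 83%) fit a comparison of two proportions, but the planned test is a Poisson regression of visit counts, with base-case power of about 57%, 63% or 85% at 57 per arm

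*Protocol*

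**What the plan says.** Protocol section 14.0 gives three safety powers. The base case reads "assuming an event rate of 25% at 1 month (estimated based on local hospital readmission rates), our sample size will provide 80% power" for a relative risk of 2. The second case reads "with an event rate of 35% we would have 98% power for risk ratio of 2.0 and 83% power for risk ratio of 1.75". The section names no test for these figures and does not say whether they refer to 57 or 66 per arm. It does say "To account for a projected dropout rate of 15%, 66 subjects will be enrolled in each group".

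Protocol section 13.0 states the analysis: the endpoint is to be "compared as the number of unplanned medical visits over the study period tested using Poisson regression". It does not say how standard errors will be computed. The SAP copies this sentence unchanged, but its copy of section 14.0 stops before the safety paragraph.

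The endpoint itself is described in two ways. Section 5.0 has "Presentation for unplanned medical care in any setting within 28 (+/-2) days", which can be read as yes or no per patient. Section 1.0 has "Key safety endpoints will be the rate of unplanned medical care" and lists what counts: "presentation to ED or urgent care, unplanned hospitalization, unplanned medical office visit".

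**The concern.** Section 14.0 speaks of risks and risk ratios, which belong to the share of patients with an event. Section 13.0 tests how many visits occur. A visit count and a yes/no outcome carry different information, and a ratio of shares is not a ratio of visit rates, so a power worked out for one does not carry over to the other. Neither document connects the two.

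At stake is how a null safety result would be read: the reader cannot tell what chance a doubling of unplanned care had of being shown. There is a second consequence. Model-based Poisson standard errors assume that variance equals mean. If visits cluster within patients they are too small and false positives rise; if each patient has at most one visit they are too large and the test is too cautious. Clustering is plausible here, since an ED presentation that ends in admission fits two items on the section 1.0 list, and the documents do not say whether it counts once or twice.

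**Working it through.** **Inputs.** From section 14.0: control rates 25% and 35%, ratios 2.0 and 1.75, 57 per arm evaluable and 66 enrolled (66 × 0.85 = 56.1 after dropout). From section 1.0: 1:1 allocation. Two-sided 0.05 is stated for the heart-rate test and assumed here for safety. Results are in the order 25% × 2.0, 35% × 2.0, 35% × 1.75; the plan states 80/98/83%.

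**Step 1: reproduce the stated powers as two proportions.**

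- 57 per arm, unpooled, uncorrected: power = Φ(|p2 − p1|/SE − 1.96). For 25% vs 50%, SE = √[(0.1875 + 0.25)/57] = 0.0876, and 0.25/0.0876 − 1.96 = 0.89, which gives 81.4%. All three: **81.4/97.9/82.8%**.
- 66 per arm, continuity-corrected: (0.25 − 1/66 − 1.96 × 0.0843)/0.0814 = 0.856, which gives 80.4%. All three: **80.4/97.8/82.0%**.

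Either version is within 2 points of every stated figure.

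**Step 2: power of the planned test.** For Poisson regression with two arms and equal follow-up, power = Φ(ln(r2/r1)/SE − 1.96), with SE = √[1/(n·r1) + 1/(n·r2)] and r the mean visits per patient. If p is the share with at least one visit, r = −ln(1 − p) for Poisson counts. Base case at n = 57:

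- **Reading A**, the percentage is mean visits: r = 0.25 and 0.50; SE = √(1/14.25 + 1/28.5) = 0.324; 0.693/0.324 − 1.96 = 0.18; power 57.0%.
- **Reading B**, 25% is the control share and the visit rate doubles: r = 0.288 and 0.575; SE = 0.302; 0.693/0.302 − 1.96 = 0.33; power 63.0%.
- **Reading C**, the share itself doubles to 50%: r = 0.288 and 0.693, a rate ratio of 2.41; SE = 0.294; 0.879/0.294 − 1.96 = 1.03; power 84.9%.

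| Poisson test of counts | n = 57 per arm | n = 66 per arm |
|---|---|---|
| Stated (n not given) | 80/98/83 | 80/98/83 |
| A | 57.0/71.5/51.4 | 63.3/77.6/57.4 |
| B | 63.0/80.1/60.0 | 69.4/85.5/66.3 |
| C | 84.9/99.2/90.0 | 89.6/99.7/93.7 |

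Simulation of the same Wald test gives values 0 to 3 points higher. No row gives the stated set.

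**Step 3: standard errors.** The following is simulated under no difference at 57 per arm, with a mean of 0.25 visits. Suppose a share q of presentations counts as two visits; then variance/mean = (1 + 3q)/(1 + q). The shares and dispersions are assumptions, because the documents give none.

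| Assumption | Variance/mean | Type I error, model-based | Type I error, robust |
|---|---|---|---|
| q = 1/4 | 1.40 | 8.9% | 5.0% |
| q = 1/3 | 1.50 | 10.2% | 5.1% |
| q = 1/2 | 1.67 | 12.2% | 4.8% |
| Gamma-Poisson counts | 2.00 | 15.1% | 6.5% |
| At most one visit per patient | 0.75 | 2.1% | 4.1% |

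Without clustering, model-based error is about 5%.

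**The case against.** The strongest reply is that no shortfall appears on the reading the wording favours. Section 14.0 speaks of risks and readmission rates, so shares of patients, and section 5.0 can be read as yes/no. That points to reading C, where the planned test has more power than stated. Readings A and B treat a risk ratio as a rate ratio.

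In addition, reading C with robust errors, gamma-Poisson counts and an assumed variance/mean of 1.6 to 1.75 gives 78–80/98–99/83–85% at 57 per arm, near the stated set. A yes/no endpoint analysed by Poisson regression with robust errors gives 78.1/96.9/80.6% at 57 and 83.8/98.3/85.5% at 66, also near it. Neither two-proportion version rounds exactly to all three stated figures, so their origin is inferred. The type I error figures rest on assumed clustering and on a variance method the plan does not specify. And little depends on safety power.

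Much of this stands. Reading C does fit best, the plan's figures are then conservative, and the consequences are limited. But section 1.0 calls the endpoint a rate, section 13.0 tests counts, and Poisson regression estimates a rate ratio, so A and B remain open. The combinations that rescue the stated powers need a dispersion, robust errors or a yes/no outcome, none of which the plan states for this analysis.

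**Conclusion.** The concern holds. The stated powers are not miscalculated for two proportions, but they do not describe the planned test. In the base case that test has about 57%, 63% or 85% power at 57 per arm, and 63%, 69% or 90% at 66, against a stated 80%. This assumes two-sided 0.05, equal follow-up and Poisson counts without clustering. The direction of the error cannot be settled from the documents. The unstated standard error is a related gap: under the assumptions shown, type I error with model-based errors runs from about 2% to 15%, against about 4% to 6.5% with robust errors.

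Importance is minor to moderate. Heart rate set the sample size, and the SAP reports 19 of 132 subjects and that "formal statistical analysis was not completed due to low sample size". The point matters for any later report, which the SAP leaves open, and for reuse of the design.

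**What to change.** For any later report or reuse of the design:

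1. In section 13.0, and in the SAP's copy of it, specify Poisson regression with robust (sandwich) standard errors and, as long as visits are counted, a log follow-up-time offset. State whether an ED presentation that leads to admission counts once or twice.
2. In section 14.0, state whether 25% and 35% are shares of patients or mean visits, and whether 2.0 and 1.75 are ratios of shares or of visit rates. Restate the three powers for the planned test, naming the test and the number per arm after dropout (about 56 to 57).
3. If the endpoint is meant to be at least one visit per patient, say so in section 13.0. The robust Poisson risk ratio then keeps power close to the stated figures, at the loss of information on repeat visits.

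The change is wording only and adds no patients. Intervals widen somewhat if visits cluster, and the restated power may be less favourable: at 57 per arm with robust errors and an assumed variance/mean of 1.5, base-case power is about 42–44% under reading A and 81–84% under reading C.

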15.0 Institutional Review Board

The conduct of this study will conform to the International Conference on Harmonization Good Clinical Practice (ICH-GCP) guidelines and applicable regulations. A copy of the protocol (including protocol amendments), and all versions of informed consent forms will be sent to IRB for approval of both of the participating centers prior to implementation of the study. The investigator will also obtain IRB approval of the annual continuing review throughout the duration of the study and will notify the IRB of deviations from the protocol.

16.0 Informed Consent Process

All participants or their family members will be given detailed oral and written information about the study. Consent forms describing in detail the study procedures and risks will be given to each participant or their family members and written documentation of informed consent is required prior to enrollment. Participants or their family members must sign an informed consent document that has been approved by the IRB. The informed consent form will be signed and dated by the participant, and the person who conducted the informed consent discussion. The original signed informed consent form will be retained in the participant's study file and a copy will be provided to the participant. Participants may withdraw consent at any time during the course of the study. Deciding to not be part of the study will not change the patient's regular medical care in any way.

17.0 Participant Confidentiality

All subject related information including Case Report Forms, and biological specimens will be kept strictly confidential. All records will be kept in a secure, locked location and only research staff will have access to the records. Subjects will be identified only by means of a coded number specific to each

subject. All computerized databases will identify subjects by numeric codes only, and will be password protected.

18.0 Data Management and Source Documentation

Research staff will collect data on study specific case report forms (CRFs). Source documentation will support the data collected on the CRFs. Source documents include all recordings of observations or notations of clinical activities and all reports in the EMR. All de-identified data will be entered in the password-protected, HIPAA compliant, REDCap database (Research Electronic Data Capture <http://project-redcap.org/>).

STATISTICAL ANALYSIS PLAN: OBSERVE-IVA

A Randomized, Double-Blind, Placebo-Controlled Trial
Assessing the Efficacy of Ivabradine Initiated at the
Time of Discharge from the Observation Unit

NCT: 03168529
8/1/2021

[name]
[contact]

Statistical Analysis Plan:

**A Randomized, Double-Blind, Placebo-Controlled Trial Assessing the Efficacy of Ivabradine Initiated at the Time of Discharge from the Observation Unit.
(OBSERVE-IVA)**

NCT: 03168529

The original plan detailed in the protocol is as follows:

13.0 Statistical Analysis The primary outcome (change in heart rate i.e. the value at Day 28 (+/-2) - the value at baseline) will be analyzed as two sample t-test. Secondary outcomes that are continuous variables will be analyzed as two sample t-test. The safety endpoint of unplanned visits will be compared as the number of unplanned medical visits over the study period tested using Poisson regression.

14.0 Sample Size And Power Based on the SHIFT1 study, the mean heart rate reduction with IVA is 8 bpm with a standard deviation of 13 bpm. A sample size of 57 in each group will have 90% power to detect a difference in means of 8.0 assuming that the common standard deviation is 13.0 using a two group t-test with a 0.05 two-sided significance level. To account for a projected dropout rate of 15%, 66 subjects will be enrolled in each group (132 total for the study over a 2-year period). Furthermore, we expect that our centers will recruit a cohort that is 75% self-identified African Americans. This number (n=99) will provide 80% power to detect the same effect size when analyzed in African Americans only.

Unfortunately, formal statistical analysis was not completed due to low sample size. Unfortunately, OBSERVE IVA fell far short of its enrollment goal with just 19 out of a targeted 132 subjects included in the final study cohort. Because of this, we have not developed any abstracts, manuscripts or other publications to date, though we may do so in the future. Of the 19 enrollments, 6 were at Detroit Receiving Hospital, 8 at Sinai-Grace Hospital, 2 at Harper University Hospital, and 3 at Henry Ford Hospital. A total of 13 subjects (68%) received ivabradine (IVA) and 6 received matching placebo.

Baseline data for the overall study cohort and by randomization are provided in the accompanying **Table** with corresponding notation regarding the approach to statistical analysis. While no formal comparison has been performed, data showing heart rate at each of the 3 study visits for the 19 subjects enrolled and by study group are provided in the accompanying **Figure**.

Table: Baseline data for OBSERVE IVA study cohort

Figure: Heart rate trends by study visit (1= baseline, 2 = 15 days, 3 = 30 days)
